5. GENERAL METHODOLOGY AND CONVENTIONS

CIs for all endpoints in the statistical analysis will be presented as 2-sided at the 95% level unless specified otherwise.

The safety analyses are based on the safety populations. Participants will be summarized by vaccine group according to the study interventions they actually received. Completely missing reactogenicity e-diary data will not be imputed; missing AE dates will be handled according to the Pfizer safety rules.

For all the immunogenicity endpoints, the analysis will be based on the evaluable immunogenicity population.

An additional analysis may be performed based on the mITT population if there is a large enough difference in sample size between the mITT population and the evaluable immunogenicity population. Participants will be summarized according to the vaccine group to which they were randomized. Missing serology data will not be imputed.

5.1. Hypotheses and Decision Rules

There are no statistical hypotheses in the study.

5.2. General Methods

Descriptive summary statistics will be provided for all endpoints. Unless otherwise explicitly stated, descriptive statistics for the continuous variables are n, mean, median, standard deviation, minimum, and maximum. Descriptive statistics for the categorical variables are the proportion (%) and the numerator (n) and the denominator (N) used in the calculation of the proportion.

All safety and immunogenicity summaries will be presented by vaccine group unless otherwise explicitly stated. The data from initial and expanded enrollments will be analyzed separately. The same analyses will be repeated for expanded enrollment as those in initial enrollment.

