2. INTRODUCTION

2.1. Study Rationale

This is a Phase 1/2 randomized study to evaluate the safety, tolerability, and immunogenicity of a modRNA vaccine against influenza in healthy individuals. This study will be conducted across 2 substudies – Substudy A and Substudy B. Substudy A will describe the safety and immunogenicity of mIRV A or B at 4 dose levels, bIRV encoding both A and B strains in the dose-level combinations shown in Table 5, and qIRV encoding 2 A strains and 2 B strains at a dose level of CCI. Additionally, Substudy A will describe:

- The immune response elicited by licensed QIV following prior receipt of a modRNA vaccine, to assess potential priming of the immune response, and
- The immune response elicited by mIRV A or B following prior receipt of licensed QIV, to assess if the immune response following QIV may be enhanced.

Safety and immunogenicity data reported to date from Substudy A are detailed in the IB. In summary, following review of the safety data from Substudy A up to 1 week following Vaccination 1 in all groups, no safety concerns have been identified. Specifically, 1-week follow-up reactogenicity data of 194 participants who received mIRV, bIRV, or qIRV in Substudy A showed most events to be mild to moderate in severity, with the most common events being pain at the injection site, fatigue, and headache.

Immunogenicity data up to 1 week following Vaccination 1 in Substudy A showed:

- The proportion of participants achieving seroconversion following administration of mIRV encoding A or B strain increased in a dose-dependent manner.
- The proportion of participants achieving seroconversion 1 week following administration of mIRV at a dose level of cell encoding A strain was 71.4% compared to 53.7% of participants having received licensed QIV.

- The proportion of participants achieving seroconversion 1 week following administration of mIRV at a dose level of CCI encoding B strain was 42.9% compared to 23.8% of participants having received licensed QIV.
- Potential interference in the immune response elicited against B strain was observed when mIRVs encoding A and B strains were combined and administered as bIRV, eg, the proportion of participants achieving seroconversion 1 week following administration of bIRV at a dose level of **CCI** encoding A strain and **CCI** encoding B strain was 6.7% for B strain compared to 25.0% of participants having received mIRV at a dose level of encoding B strain.

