10.10.4. Substudy B Design

10.10.4.1. Overall Design

This is a randomized, single-blinded (sponsor-unblinded) substudy to evaluate the safety and immunogenicity of the vaccination schedules detailed below. The design of Substudy B is summarized in Section 1.2.2.

Participants 65 to 85 years of age will be randomized to one of the following vaccination schedules at Visit 201 (Vaccination 1) and will be blinded to which 1-visit or 2-visit vaccination schedules they will receive:

2-Visit Schedules

- 2 Doses of qIRV encoding 2 A strains and 2 B strains at a dose level of administered 21 days apart.
- 2 Doses of licensed QIV, administered 21 days apart (as a control group).
- A dose of licensed QIV following by a dose of bIRV encoding 2 A strains at a dose level of either CCl administered 21 days apart.

1-Visit Schedules

- A dose of licensed QIV administered concurrently in the opposite arm with bIRV encoding 2 A strains at a dose level of either CC.

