10.10.6.1.1. Administration

See Section 6.1.1.

During Substudy B, participants will receive study intervention as randomized at Visit 201 and, if applicable, at Visit 203 in accordance with the SoA (Section 10.10.1).

Study intervention should be administered intramuscularly as detailed in Table 6.

 Table 6.
 Substudy B Study Intervention Schedule

Participant	Vaccine	Study Intervention	- Vaccination 1	Study Intervention -	Vaccination 2
Age	Group	Right Deltoida	Left Deltoid	Right Deltoida	Left Deltoid
	1	qIRV CCI		qIRV CCI	
		2 x A, 2 x B		2 x A, 2 x B	
		CCI		CCI	
	2	Licensed QIV		bIRV CCI	
				2 x A CC	
	3	Licensed QIV		bIRV CC	
				2 x A CC	
	4	Licensed QIV		Licensed QIV	
	5	bIRV CC	Licensed QIV		
65.		2 x A CC			
65 to	6	bIRV CC	Licensed QIV		
85 years of		2 x A CC			
age		qIRV CCI			
	7	$2 \times A, 2 \times B$			
		CCI			
	8	Licensed QIV			
		bIRV CC	bIRV CC		
	9		2 x A		
		2 x B CC	CCI		
		qIRV CC			
	10	2 x A CC			
		2 x B CC			

PFIZER CONFIDENTIAL

Table 6. Substudy B Study Intervention Schedule

Participant	Vaccine	Study Intervention - Vaccination 1		ne Study Intervention - Vaccination 1 Study Intervention	Study Intervention -	Vaccination 2
Age	Group	Right Deltoid ^a	Left Deltoid	Right Deltoida	Left Deltoid	
	11	qIRV CCI 2 x A CCI 2 x B CCI				
	12	Licensed QIV			Placebo	
18 to	13	qIRV CCI 2 x A, 2 x B				
64 years of age	14	qIRV CCI 2 x A, 2 x B				

a. Local reactions will be assessed at the injection site on the right deltoid (see Section 8.2.3.2).

Study intervention in Substudy B will be administered in a single-blinded manner.

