2.3. Study Design

2.3.1. Overall Design

This is a Phase 1/2 randomized, single-blinded (sponsor-unblinded) study to evaluate the safety, tolerability, and immunogenicity of a modRNA vaccine against influenza in healthy individuals from 18 through 85 years of age.

In participants from 65 through 85 years of age:

Participants will be randomized to and will be blinded to which 1-visit or 2-visit vaccination schedules they will receive:

2-Visit Schedules

- 2 Doses of qIRV encoding 2 A strains and 2 B strains at a dose level of CCl
 administered 21 days apart
- 2 Doses of licensed QIV, administered 21 days apart (as a control group)
- A dose of licensed QIV following by a dose of bIRV encoding 2 A strains at a dose level of either CCl administered 21 days apart

1-Visit Schedules

- A dose of licensed QIV administered concurrently in the opposite arm with bIRV encoding 2 A strains at a dose level of either CC
- A dose of bIRV encoding 2 A strains at a dose level of CCl administered concurrently in the opposite arm with bIRV-encoding 2 B strains at a dose level of CCl
- A dose of qIRV encoding 2 A strains and 2 B strains at the following dose level combinations:

• A dose of licensed QIV (as a control group)

Substudy B enrollment will be separated into an initial and expanded enrollment. Depending on the availability of study intervention and operational prioritization, groups in Substudy B may not all be randomized concurrently; however, a minimum of 2 groups will be open for randomization at any 1 time.

During initial enrollment, each group (vaccine formulation/dose level, or control) will comprise 15 participants. Hence, Substudy B initial enrollment will comprise approximately 165 participants.

Substudy B expanded enrollment will comprise group(s) of 120 participants following the vaccination schedule(s) as selected by the sponsor's IRC from initial enrollment. If deemed acceptable, an additional 120 participants will be enrolled in that group (expanded enrollment). Additionally,

- Expanded-enrollment groups may also be included that comprise only the first dose from 2-visit—schedule initial-enrollment groups, eg, 1 dose of qIRV at a dose level of CCI.
- A control group of 120 participants will be enrolled during expanded enrollment who will receive a dose of licensed QIV followed by placebo, administered 21 days apart.

In participants from 18 through 64 years of age:

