6.1.1.1.1. Main Analysis

- Estimand: The percentage of participants reporting local reactions (redness, swelling, and pain at the injection site) for up to 7 days following each vaccination (Section 3.1.1.1).
- Estimand strategy: Treatment policy (Section 2.2.1).
- Analysis set: Safety population for 1-visit schedules and Vaccination 1 safety population or Vaccination 2 safety population for 2-visit schedules (Section 4).
- Analysis time point: Day 1 through Day 7 after each vaccination. Refer to Section 3.1.1.1 for maximum severity.
- Analysis methodology: Descriptive summary statistics.
- Intercurrent events and missing data: The participants without any e-diary data throughout the 7 days after each vaccination will be excluded from the analysis at that particular vaccination. For participants who discontinue, all collected data will be included; intermediate missing values will not be imputed.
- Reporting results: The proportion, the numerator (n) and denominator (N) used for the calculation of the proportion, and associated 2-sided Clopper-Pearson 95% CI will be presented, by vaccine group, for the following variables:
 - o Presence or absence of each local reaction on each day (Day 1-7) after vaccination.
 - o Presence or absence of each local reaction on "any day (Day 1-7)" after vaccination.
 - o Presence or absence of any local reaction on "any day (Day 1-7)" after vaccination.
 - o Maximum severity of each local reaction on "any day (Day 1-7)" after vaccination.
- The n, mean, standard deviation, median, minimum, and maximum will be presented by vaccine group, for the following variables:
 - O Duration of each local reaction after vaccination.

- Onset day of each local reaction after vaccination.
- Onset day of any local reaction after vaccination.

Figures:

Bar charts with the proportions of participants for each local reaction throughout 7 days will be plotted by vaccine group. The bars will be divided into severity categories to highlight the proportions of participants by maximum severity.

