6.2. Secondary Endpoints

- 6.2.1. HAI Titers for Each Strain Targeted by the Study Vaccine
- 6.2.1.1. Participants From 65 Through 85 Years of Age
- 6.2.1.1.1 The Analyses in Sections 6.2.1.1.1 to 6.2.1.1.4 are for Participants From 65 Through 85 Years of Age HAI GMTs at Each Scheduled Visit

6.2.1.1.1.1. Main Analysis

- Estimand: HAI GMTs before Vaccination 1, prior to Vaccination 2 (Day 21, if applicable), and at 1, 4, and 8 weeks after the last vaccination.
- Estimand strategy: Hypothetical strategies (Section 2.2.2).
- Analysis set: Evaluable immunogenicity population (Section 4).
- Analysis time points: Day 1 before Vaccination 1, prior to Vaccination 2 (Day 21, if applicable), and at 1, 4, and 8 weeks after the last vaccination.
- Analysis methodology: Descriptive summary statistics.
- Intercurrent events and missing data: Missing immunogenicity results will not be imputed, as MCAR is assumed. For participants who discontinue or have major protocol violations, all postdiscontinuation or postviolation observations will be censored.
- Reporting results: HAI GMTs (Section 5.2.2.1) and associated 2-sided 95% CIs will be provided by vaccine group and strain(s) before Vaccination 1, prior to Vaccination 2 (Day 21, if applicable), and at 1, 4, and 8 weeks after the last vaccination.

Figures:

• Empirical RCDCs (Section 5.2.2.4) will be provided for HAI GMTs by vaccine group and strain(s) before Vaccination 1, prior to Vaccination 2 (Day 21, if applicable), and at 1, 4, and 8 weeks after the last vaccination.

• HAI GMTs and associated 95% CIs will be plotted by vaccine group and strain(s) before Vaccination 1, prior to Vaccination 2 (Day 21, if applicable), and at 1, 4, and 8 weeks after the last vaccination.

6.2.1.1.2. HAI Geometric Mean Fold Rises After Receipt of Vaccination 1

6.2.1.1.2.1. Main Analysis

- Estimand: HAI GMFRs from before Vaccination 1 to prior to Vaccination 2 (Day 21, if applicable) and to 1, 4, and 8 weeks after receipt of the last vaccination.
- Estimand strategy: Hypothetical strategies (Section 2.2.2).
- Analysis set: Evaluable immunogenicity population (Section 4).
- Analysis time points: Day 1 before Vaccination 1 (baseline for calculation) to prior to Vaccination 2 (Day 21, if applicable) and to 1, 4, and 8 weeks after receipt of the last vaccination.
- Analysis methodology: Descriptive summary statistics.

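### In initial enrollment, three groups share one blinded first dose of licensed QIV, but the legible SAP shows their Vaccination 1 reactions only as separate groups of about 15

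*SAP*

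**What the plan says.** Protocol 10.10.4.1 describes the schedule of Groups 2 and 3 as "A dose of licensed QIV following by a dose of bIRV encoding 2 A strains at a dose level of either" of two levels, 21 days apart. Group 4 receives licensed QIV twice at the same interval. Table 6 (protocol 10.10.6.1.1) places the first QIV dose of all three groups in the right deltoid, with nothing in the left. Local reactions are read on the right arm only. Participants stay blinded to their schedule (10.10.6.2.2).

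On size, SAP 2.3.1 states: "During initial enrollment, each group (vaccine formulation/dose level, or control) will comprise 15 participants".

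On reporting, the general rule in SAP 5.2 is "All safety and immunogenicity summaries will be presented by vaccine group unless otherwise explicitly stated". SAP 6.1.1.1.1 repeats it for local reactions after each vaccination: "associated 2-sided Clopper-Pearson 95% CI will be presented, by vaccine group, for the following variables". Systemic events are handled in the same way. SAP 5.2 also analyzes initial and expanded enrollment separately. SAP 4 defines a Vaccination 1 safety population for 2-visit schedules, but its summaries remain by vaccine group. Summaries across groups appear only for demographics, medical history, disposition and concomitant treatments (SAP 6.5).

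**The concern.** Until Vaccination 2, Groups 2, 3 and 4 are by design one treatment group. Their Vaccination 1 e-diary outcomes estimate the same quantity, yet the tables will show three separate values, each with the interval of a group of 15.

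Two things are at stake. First, the QIV reference for a first dose on a 2-visit schedule, the natural comparator for the first qIRV dose in Group 1, is less precise than the data allow. SAP 5.2.1.1 provides for between-group differences in safety proportions, although it does not say which groups will be compared. Second, chance differences between three identical columns may be read as real when the internal review committee looks at initial-enrollment data to choose groups for expansion.

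**Working it through.** **Inputs.** There are 15 participants per group in initial enrollment (SAP 2.3.1). Intervals are exact two-sided 95% Clopper-Pearson (SAP 5.2.1). The documents give no expected first-dose QIV reaction rate, so rates of 0%, 20% and 53% are assumed. The 53% is close to the maximum interval width. It is near a Substudy A result, "71.4% compared to 53.7% of participants having received licensed QIV" (protocol 2.1), but that is a 1-week seroconversion rate and serves here only as an illustration.

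**The plan's own figures.** Protocol Table 4 uses 1 − (1 − p)^n. At p = 5%, n=15 gives 1 − 0.95^15 = 0.537 (stated 0.54), and n=45 gives 1 − 0.95^45 = 0.901 (stated 0.9). Both reproduce.

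**Interval for the first-dose QIV rate**

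| Pool | n | Near 53% | Width (points) | At 20% | Width (points) | Upper limit, no events |
|---|---|---|---|---|---|---|
| One group | 15 | 8/15: 26.6–78.7% | 52.1 | 3/15: 4.3–48.1% | 43.8 | 21.8% |
| Two of Groups 2–4 | 30 | 16/30: 34.3–71.7% | 37.3 | 6/30: 7.7–38.6% | 30.9 | 11.6% |
| Groups 2–4 | 45 | 24/45: 37.9–68.3% | 30.5 | 9/45: 9.6–34.6% | 25.0 | 7.9% |
| Groups 2–4 and 8 | 60 | 32/60: 40.0–66.3% | 26.3 | 12/60: 10.8–32.3% | 21.5 | 6.0% |

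Group 8 (a single dose of licensed QIV, right deltoid) can join for Vaccination 1 reactions if it was randomized at the same time.

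**Contrast with Group 1 (n=15).** With equal variance, the ratio of standard errors, pooled to unpooled, is √[(1/15 + 1/m) ÷ (2/15)]. For m=30 this is 0.866, a fall of 13%. For m=45 it is 0.816, a fall of 18%.

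**Chance spread.** With a true rate of 53% in all three groups of 15, the highest and lowest observed rates differ by at least 20 points (3 of 15) with probability 0.63, and by at least 26.7 points (4 of 15) with probability 0.40. At a true rate of 20% the probabilities are 0.48 and 0.24.

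**Day 21 titers.** SAP 6.2.1 plans these too: "HAI GMTs (Section 5.2.2.1) and associated 2-sided 95% CIs will be provided by vaccine group and strain(s) before Vaccination 1, prior to Vaccination 2". The analysis set is the obstacle. The evaluable immunogenicity population (SAP 4) requires all vaccines as randomized, a valid result 26–35 days after the last vaccination, and no major violation. The mITT population requires a result after the last vaccination. Membership of either set is settled after the groups have diverged, so the Day 21 results in these sets are not a clean first-dose comparison.

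**The case against.** The strongest reply is that this is a matter of presentation in a descriptive study without hypotheses. The tables must give n and N, so a reader can add three columns and compute the pooled interval. That is true for a single proportion. It leaves the choice of groups to pool until after the data are seen, by a sponsor who is unblinded throughout (protocol 10.10.6.2.3). The by-group columns remain under the fix, so a pooled column gives a reader the right reference but does not prevent overreading.

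Several limits stand. Groups need not be randomized concurrently, and only two need be open at once (protocol 10.10.4.1). The amendment history shows that the schedules of Groups 2–4 entered together, not that they enrolled together. Group 8 came one amendment later. The n=15 problem belongs to initial enrollment: an expanded group has 120, with a width of 18.5 points at 64/120. Content is missing from the exploratory sections, so pooling there cannot be ruled out.

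A reader might go further and infer that separate reporting weakens planned Day 21 comparisons, or blurs what the second dose adds. The documents do not support either. The legible Substudy B secondary estimands are within-group, and the synopsis places the comparisons with QIV at 4 weeks after vaccination. What the second dose adds is a within-participant change from that person's own Day 21 titer, which a pooled Day 21 mean does not sharpen.

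**Conclusion.** The point holds for Vaccination 1 reactogenicity in initial enrollment. Reporting identical first-dose QIV recipients only by group makes the interval for a rate near 53% about 1.4 times as wide as a pool of two groups would give (52.1 ÷ 37.3), and about 1.7 times as wide as a pool of three (52.1 ÷ 30.5). With no events the upper limit is 2.8 times as high as with three (21.8 ÷ 7.9). The gain for a contrast with one group of 15 is modest, at 13–18%.

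This rests on full groups of 15 with e-diary data, on at least two of Groups 2–4 having been randomized concurrently, and on the assumed rates. It is a loss of precision and not an error in any test. It does not extend to Day 21 titers as the analysis sets now stand.

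**What to change.** In SAP 5.2, add a pooled column, *licensed QIV, first dose*, beside the by-group columns for Vaccination 1 local reactions, systemic events and immediate AEs. Use the Vaccination 1 safety population and combine those of Groups 2, 3 and 4 that were randomized concurrently. Add Group 8, from the safety population, if it was concurrent. Immediate AEs must be restricted to those after Vaccination 1, because SAP 6.1.1.3 covers the whole period from the first vaccination to 4 weeks after the last. Apply the same rule within expanded enrollment to groups that share the QIV first dose, and define concurrency before the data are reviewed.

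A pooled Day 21 HAI column for Groups 2–4 may be added as a descriptive summary only on a set fixed before divergence: randomized, received Vaccination 1 as assigned, valid baseline and pre-Vaccination 2 results, and no major violation before Vaccination 2. It should not be presented as strengthening Day 21 contrasts or the estimate of the second dose's effect.

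The cost is SAP wording and one table column, plus one further analysis set if the Day 21 option is taken. No new data are needed. The one small downside is that the pool must be confined to the same enrollment period, which may leave fewer than 45.

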9.5. Sample Size Determination

The study sample size for the study is not based on any statistical hypothesis testing.

Fifteen participants will be enrolled in each group (vaccine formulation/dose level or control) for Vaccination 1 in Substudy A, and also into each group for Vaccination 1 in Substudy B. There are 17 such groups planned to be enrolled in Substudy A; therefore, up to approximately 255 participants in total are planned to be enrolled in Substudy A.

During initial enrollment, there are 11 groups for Vaccination 1 in Substudy B, with approximately 15 participants planned to be enrolled per group. Additionally, following IRC review of safety and immunogenicity at least 1 week following the last vaccination in each group from initial enrollment, a further 120 participants may be enrolled in selected groups, including 2 groups of participants 18 to 64 years of age (expanded enrollment). Therefore, up to approximately 1725 participants are planned to be enrolled in Substudy B.

For safety outcomes in the study, Table 4 shows the probability of observing at least 1 AE for a given true event rate of a particular AE, at various sample sizes.

Table 4. Probability of Observing at Least 1 AE by Assumed True Event Rates With Different Sample Sizes

			Assumed T	True Event Ra	ate of an AE		
Sample Size (N)	0.01%	0.32%	0.50%	1.0%	2.0%	5%	10%
15	0.00	0.05	0.07	0.14	0.26	0.54	0.79
30	0.00	0.09	0.14	0.26	0.45	0.79	0.96
45	0.00	0.13	0.2	0.36	0.6	0.9	0.99
60	0.01	0.17	0.26	0.45	0.7	0.95	>0.99
90	0.01	0.25	0.36	0.6	0.84	0.99	>0.99
120	0.01	0.32	0.45	0.7	0.91	>0.99	>0.99
135	0.01	0.35	0.49	0.74	0.93	>0.99	>0.99
150	0.01	0.38	0.53	0.78	0.95	>0.99	>0.99
195	0.02	0.46	0.62	0.86	0.98	>0.99	>0.99
270	0.03	0.58	0.74	0.93	>0.99	>0.99	>0.99
275	0.03	0.59	0.75	0.94	>0.99	>0.99	>0.99
410	0.04	0.73	0.87	0.98	>0.99	>0.99	>0.99
420	0.04	0.74	0.88	0.99	>0.99	>0.99	>0.99
445	0.04	0.76	0.89	0.99	>0.99	>0.99	>0.99
540	0.05	0.82	0.93	>0.99	>0.99	>0.99	>0.99
695	0.07	0.89	0.97	>0.99	>0.99	>0.99	>0.99
815	0.08	0.93	0.98	>0.99	>0.99	>0.99	>0.99
945	0.09	0.95	0.99	>0.99	>0.99	>0.99	>0.99
1080	0.10	0.97	>0.99	>0.99	>0.99	>0.99	>0.99
1215	0.11	0.98	>0.99	>0.99	>0.99	>0.99	>0.99
1350	0.13	0.99	>0.99	>0.99	>0.99	>0.99	>0.99
1485	0.14	0.99	>0.99	>0.99	>0.99	>0.99	>0.99

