5.2.1.1. Safety Data

All safety analyses will be performed on the safety populations.

For safety data, as defined in Section 3.1.1, the exact 2-sided 95% CIs using the Clopper and Pearson method will be provided by vaccine group for all primary safety endpoints and for proportions of participants reporting local reactions, systemic events, AEs (including immediate AEs), SAEs, abnormal troponin I values, and new ECG abnormalities. The 95% CI for the between-group difference for binary endpoints will be calculated using the Miettinen and Nurminen method.

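### No planned Substudy B summary of AEs, SAEs, troponin I or ECG abnormalities has a denominator above 120; labelled pooled summaries of the rare serious and cardiac events would be a cheap addition

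*SAP*

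**What the plan says.** SAP 5.2 sets the reporting unit: "All safety and immunogenicity summaries will be presented by vaccine group unless otherwise explicitly stated". The same section then splits by stage: "The data from initial and expanded enrollments will be analyzed separately". SAP 5.2.1.1 repeats the unit for the exact intervals, which "will be provided by vaccine group for all primary safety endpoints". The primary safety analyses in SAP 6.1.1.1 to 6.1.1.6 all report by vaccine group, and SAP 6.4 plans no subset analyses.

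Group sizes are in SAP 2.3.1: "During initial enrollment, each group (vaccine formulation/dose level, or control) will comprise 15 participants", and "Substudy B expanded enrollment will comprise group(s) of 120 participants". The 240 participants aged 18 to 64 are randomized 1:1, so 120 per group, in expanded enrollment only. On intervals, SAP 5 says "CIs for all endpoints in the statistical analysis will be presented as 2-sided at the 95% level".

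Protocol 9.5 says "The study sample size for the study is not based on any statistical hypothesis testing". Its quantitative support is a look-up table: "Table 4 shows the probability of observing at least 1 AE for a given true event rate of a particular AE". That table runs from N = 15 to N = 1485 and names no analysis for any row.

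Protocol 2.3.1 gives myocarditis and pericarditis as a risk of the modRNA platform. Protocol 8.3.8 and SAP 3.1.1.5 make them AESIs.

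**The concern.** The primary objective of Substudy B is to describe safety, and the events of most interest are uncommon. A table of 15 or 120 participants with no cardiac event says little about such events, because the upper confidence limit stays at several percent. The trial will hold data on several hundred to well over a thousand modRNA recipients, yet the SAP produces no safety endpoint summary that uses them together. Even the same regimen across its two stages (15 + 120 = 135) is never summarized as one group. SAP 6.1.1.3 lists any, immediate, severe and related AEs and those leading to withdrawal, but no AESI summary, pooled or otherwise. A reader of the report would have to add up counts across tables and compute the intervals.

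**Working it through.** **Inputs.** Group sizes of 15 and 120 (SAP 2.3.1). Eleven initial groups and up to 13 expanded groups (protocol 1.1 and 9.5). Regimens from protocol Table 6. Minimum Substudy B enrollment of 645 (SAP 2.3.1). Exact (Clopper-Pearson) two-sided 95% intervals (SAP 5.2.1).

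**1. The plan's own figures.** The chance of at least one event is 1 − (1 − p)^N. At p = 1.0% this gives 0.14 for N = 15, 0.70 for N = 120 and 0.74 for N = 135, as Table 4 prints. All 154 cells (22 sizes by 7 rates) reproduce. The Substudy B total also reproduces: 11 × 15 + 13 × 120 = 165 + 1560 = 1725.

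**2. Largest planned denominator.** With reporting by group and by stage, it is max(15, 120) = 120. Sixteen of the 22 rows of Table 4 (135 to 1485) exceed it.

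**3. Size of the modRNA pool.** Of the 11 initial groups in Table 6, Groups 4 and 8 receive only QIV, which leaves 9 with modRNA. Groups 13 and 14 (ages 18 to 64) add 240.
- Maximum, if all nine expand: 9 × 135 + 240 = 1215 + 240 = 1455.
- Minimum: 645 = 165 + 240 + 240, so two groups aged 65 to 85 expand. If these are one modRNA group and the QIV/placebo control, the pool is 9 × 15 + 120 + 240 = 495.

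**4. What each denominator supports.** The upper limit with zero events is 1 − 0.025^(1/N). Detection is 1 − (1 − 0.0032)^N, using the 0.32% rate of Table 4.

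| Summary | N | Upper limit, 0 events | P(at least 1) at 0.32% |
|---|---|---|---|
| One group, initial | 15 | 21.8% | 0.05 |
| One group, expanded | 120 | 3.03% | 0.32 |
| One group, both stages | 135 | 2.70% | 0.35 |
| All modRNA, ages 18 to 64 | 240 | 1.53% | 0.54 |
| All modRNA, ages 65 to 85, minimum (135 + 120) | 255 | 1.44% | 0.56 |
| All modRNA, minimum | 495 | 0.74% | 0.80 |
| All modRNA, ages 65 to 85, maximum | 1215 | 0.30% | 0.98 |
| All modRNA, maximum | 1455 | 0.25% | 0.99 |

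Combining stages within a group changes little. Almost all the gain comes from combining modRNA recipients across groups.

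**The case against.** A reader might infer that the larger sizes in Table 4 are used by no planned evaluation. The documents do not support that.
- Table 4 covers both substudies, while this SAP covers only Substudy B.
- The Substudy A stopping rules (protocol 10.9.8.6) count all IRV groups together. That is 13 × 15 = 195, which is a Table 4 row.
- The Substudy B stopping rules (protocol 10.10.8.6) run by IRV dose level, and protocol 10.10.4.1 applies them through both stages. Several are triggered by a single event, the quantity Table 4 tabulates. Their pool sizes cannot be computed because the dose levels are redacted.
- SAP 6.5.1.1, 6.5.2.2 and 6.5.4 plan overall summaries of demographics, disposition and concomitant therapy, so some planned denominators do exceed 120.

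All of this stands. But stopping rules trigger a pause and produce no reported rate or interval, and the overall summaries are not of safety endpoints.

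A reader might also take the last row of Table 4 (0/1485 gives 0.25%) as the modRNA pool. It is not: 1485 = 11 × 135 counts the two QIV-only groups and leaves out ages 18 to 64. Nor does Table 4 promise a detection level for any table. The sample size is expressly not hypothesis-based, and the rows for 15 and 120 are present. That its rows are not matched to analyses is only missing detail.

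Three further objections have weight. Separate reporting protects against bias from selecting groups on initial-stage data. Nothing is lost, since counts and denominators are reported for each stage and could be summed. And for truly rare events pooling helps little: at a rate of 0.01%, Table 4 itself gives only 0.14 at N = 1485. These are reasons to keep the separate tables and to treat pooled ones as supplementary. They are not reasons to omit them.

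**Conclusion.** The point holds for Substudy B safety endpoints: no planned AE, SAE, troponin I or ECG summary has a denominator above 120, so zero events leaves an upper limit of 3.03% at best. Pooling all modRNA recipients would bring this to between 0.74% and 0.25%, depending on how many groups expand. Nothing in the plan is wrong; this is a cheap improvement.

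It rests on planned group sizes, since numbers by vaccine actually received may differ slightly. It also rests on the SAP default of reporting by group for ages 18 to 64, where protocol 10.10.9.3.2 does not say so. The maximum of 1455 counts only the Table 6 regimens; a first-dose-only qIRV group, which SAP 2.3.1 allows, would add 120. The minimum of 495 assumes that one modRNA group and the QIV/placebo control are the two that expand at ages 65 to 85.

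**What to change.** In SAP 5.2, keep the stage-separate tables by vaccine group. Add supplementary descriptive summaries with exact 95% intervals for SAEs, AESIs, abnormal troponin I and new ECG abnormalities:
- (a) initial and expanded enrollment combined, by vaccine group;
- (b) all participants who actually received a modRNA vaccine, overall and separately for ages 18 to 64 and 65 to 85.

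Limit any side-by-side display with QIV-only recipients to ages 65 to 85. The younger group has no QIV arm, and protocol 2.3.1 notes that the cardiac cases have occurred more often in younger men. A pooled contrast across ages would be confounded.

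The cost is a few extra tables from data already collected. Each must be labelled as mixing dose levels, schedules (AE follow-up runs to 4 weeks after the last vaccination, so it is longer in 2-visit groups), possibly strains, groups not randomized concurrently, and initial-stage data used to select groups. In the QIV-then-bIRV regimens, events before the second vaccination precede modRNA exposure and should be flagged.
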